Statistical Analysis Plan (SAP)

Study Title: Efficacy of Photobiomodulation Therapy Using 980nm Versus 635nm Diode Lasers in the Management of Myofascial Pain Syndrome (LLLT-MPS_sEMG)

ClinicalTrials.gov Identifier (NCT Number): NCT07069764

Document Date: 01 May 2025

Prepared by:

Principal Investigator: [name]

Institution: National Institute Enhanced of Laser Sciences

1. Introduction

This Statistical Analysis Plan (SAP) describes the pre-specified statistical methods and procedures that will be used to analyze data for the clinical trial entitled 'Efficacy of Photobiomodulation Therapy Using 980nm Versus 635nm Diode Lasers in the Management of Myofascial Pain Syndrome (LLLT-MPS_sEMG)'.

2. Study Objectives

Primary Objective: To evaluate the effectiveness of photobiomodulation therapy using diode lasers (980nm vs 635nm) in reducing myofascial pain.

Secondary Objectives: To assess improvements in mandibular function and muscle activity (measured using sEMG).

3. Outcome Measures

Primary Outcome: Change in pain intensity measured by the Visual Analog Scale (VAS) from baseline to post-treatment and follow-up.

Secondary Outcomes:

- Change in Maximum Mouth Opening (MMO) from baseline to post-treatment and follow-up.
- Change in Lateral and Protrusive Movements (LM, PM).
- Change in surface electromyography (sEMG) activity of masseter and temporalis muscles.

4. Statistical Methods

Normality of data distribution will be assessed using the Shapiro-Wilk test.

If data are not normally distributed, non-parametric tests will be applied.

Within-group comparisons across time points (baseline, post-treatment, follow-up) will be analyzed using the Friedman test, followed by post-hoc pairwise comparisons with Bonferroni correction if significant differences are detected.

Between-group comparisons will be conducted using the Mann-Whitney U test on change scores.

Significance will be set at $p < 0.05$.

5. Effect Size Calculations

Effect sizes will be calculated to quantify the magnitude of differences:

- Kendall's W for Friedman test results (within-group changes).
- Rank biserial correlation (r) for Mann-Whitney U test results (between-group comparisons).

6. Handling of Missing Data

If missing data occur, an intention-to-treat (ITT) approach will be applied. Sensitivity analyses may be conducted to evaluate the potential impact of missing data.

7. Interim Analyses

No interim analyses are planned for this study.

8. Software

All analyses will be performed using IBM SPSS Statistics (Version 25.0) or equivalent statistical software.

9. Approval

This SAP was finalized and approved prior to database lock and commencement of statistical analyses.

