### Patient assessment:

The patients were evaluated before treatment ,after laser applications ,at the end of treatment , and 1 month after the laser applications.(18)

Evaluation of the patient is determined by pain intensity, maximum mouth opening(MMO), lateral movements(LM), protrusive movements(PM), pressure pain threshold, electromyography activity and TMJ sounds in patients with TMDS.(1,3,4,5)

At each assessment interval, the amount of mouth opening and the range of protrusive and lateral excursive movements of the jaw were measured and recorded. To measure mouth opening, the patient was asked to open the mouth at both "maximum pain-free" and "maximum possible" conditions.

The vertical interincisal distance was then measured with a digital caliper and recorded in millimeters in patient's folder.

The right and left lateral jaw movement was measured in millimeters by detecting the horizontal distance between the midpoints of the upper and lower central incisors.

A visual analog scale (VAS) was used for calculating pain grade right before our therapy. Patients were asked to describe the degree of discomfort/pain from zero to ten, the pain scale read "no pain" and "the greatest pain possible.

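### The primary VAS outcome spans two visits with no primary visit, testing order or success rule, so a 5% type I error for the laser comparison is not established

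*SAP*

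**What the plan says.** SAP section 2 gives the primary objective as "To evaluate the effectiveness of photobiomodulation therapy using diode lasers (980nm vs 635nm) in reducing myofascial pain". Section 3 has a single primary outcome: "Change in pain intensity measured by the Visual Analog Scale (VAS) from baseline to post-treatment and follow-up".

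Section 4 covers the two kinds of comparison separately. For change over time it says "Within-group comparisons across time points (baseline, post-treatment, follow-up) will be analyzed using the Friedman test, followed by post-hoc pairwise comparisons with Bonferroni correction". For the lasers it says "Between-group comparisons will be conducted using the Mann-Whitney U test on change scores", with significance at 0.05 and no adjustment. It also says "If data are not normally distributed, non-parametric tests will be applied", but names no parametric test for the other case.

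The protocol's Pico section gives the primary outcome as pain relief, without a visit. Its Patient assessment section says patients are "evaluated before treatment ,after laser applications ,at the end of treatment , and 1 month after the laser applications", and ranks none of these. The sample is 30 patients in two groups.

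**The concern.** Taken at face value, the primary outcome produces two between-laser tests, one for each post-baseline visit, each at 0.05. Three things that would fix the error rate are missing: which visit is primary, in what order the visits are tested, and what pattern of results counts as success.

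The Bonferroni step does not fill the gap. It applies to pairs of time points within one arm after a Friedman test, and the Friedman test does not compare lasers.

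The unstated success rule decides whether the error is above or below 5%. If the lasers differ significantly at one visit and not at the other, the plan does not say whether the primary objective has been met, and the choice could be made after seeing the data.

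**Working it through.** The plan has no figure to reproduce: it gives no familywise error rate, power or sample-size derivation. The check is the type I error under each possible success rule.

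**Inputs from the documents**
- Two post-baseline VAS change scores (SAP section 3).
- Mann-Whitney test on change scores at 0.05 (SAP section 4).
- 30 patients in two groups (protocol, Patient assignment and blinding).

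**Assumptions, because the documents do not give them**
- 15 patients per arm.
- Two-sided tests.
- Correlation ρ between the two change scores of 0.5 to 0.9. The lower end has a simple basis. If baseline and both visits have equal variance σ² and a common correlation r, each change has variance 2σ²(1 − r). The two changes have covariance σ²(1 − r), so their correlation is 0.5. Visits that resemble each other more than they resemble baseline push it higher.

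**Step 1: bounds.** With two tests at 0.05, the chance of at least one false positive is at most 0.05 + 0.05 = 0.10. If the tests were independent it would be 1 − 0.95² = 0.0975.

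**Step 2: correlated z-tests.** With c the two-sided 5% critical value,

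P(either) = 1 − P(|Z₁| ≤ c and |Z₂| ≤ c), and P(both) = 0.05 + 0.05 − P(either).

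At ρ = 0.5, 0.7, 0.8 and 0.9, P(either) is 0.0907, 0.0835, 0.0781 and 0.0704. P(both) is then 0.0093, 0.0165, 0.0219 and 0.0296.

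**Step 3: the Mann-Whitney test at 15 per arm.** The exact test rejects when the smaller U is at most 64 and has true size 0.0453. The normal approximation without continuity correction rejects at 65 or below and has size 0.0502. The SAP does not say which is used, so both are shown. The simulation used bivariate normal change scores, no difference at either visit, and 400,000 trials per correlation.

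| ρ | Either visit, exact | Either visit, approximate | Either visit, t-test (assumed) | Both visits, exact | Both visits, approximate |
|---|---|---|---|---|---|
| 0.5 | 0.0834 | 0.0921 | 0.0909 | 0.0071 | 0.0082 |
| 0.7 | 0.0780 | 0.0860 | 0.0848 | 0.0130 | 0.0150 |
| 0.8 | 0.0725 | 0.0800 | 0.0787 | 0.0176 | 0.0198 |
| 0.9 | 0.0667 | 0.0734 | 0.0708 | 0.0244 | 0.0274 |

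Rounding the change scores to whole numbers (SD 2 assumed, tie-corrected approximation, 200,000 trials) gives 0.0898, 0.0844, 0.0799 and 0.0719 for either visit. Ties do not alter the picture.

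**Step 4: the ceiling of a both-visits rule.** The low both-visits figures hold only when neither visit has a difference. With a 3-SD difference at one visit and none at the other (200,000 trials), the error is 0.0451 to 0.0461 exact and 0.0497 to 0.0510 approximate, with simulation error of about 0.0005. The ceiling is therefore the size of a single test, 4.5% or 5.0%.

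**Step 5: the other rules that control the error.** A fixed sequence has the same ceiling. If the first visit has no difference, any false claim requires a false rejection there. If the first visit does have a difference, only the second test can err. Bonferroni at 0.025 per visit gives 1 − 0.975² = 0.0494 if independent, 0.0465 at ρ = 0.5 and 0.0362 at ρ = 0.9 (z-tests).

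**The case against.** The strongest reply is that no text says significance at either visit would count as success. The inflation belongs to one unstated rule, is modest even then, and disappears if both visits are required. That is correct, and it limits the conclusion: control of the error is not established, which is different from being shown to be lost. The missing interpretation of a split result remains in any case.

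A second reply is that the primary question may not be the laser comparison. The wording of SAP section 2 also admits a within-arm reading, and the protocol's Aim of the study lists the effect of 980nm on pain before the comparison with 635nm. Treating the between-laser contrast as primary, and counting two tests of it, is therefore an inference. It is the better reading: the SAP title sets one laser against the other, Pico makes one laser the intervention and the other the comparison, and SAP section 2 names the contrast. The within-arm reading would leave the between-laser tests with no stated status at all.

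A third point concerns the protocol's assessment schedule. The phrases after laser applications and at the end of treatment could be one visit or two. Because SAP section 4 lists only two post-baseline time points, this is mainly a question of labels and does not clearly add a third test.

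Finally, the choice between a fixed sequence, a both-visits rule and an alpha split is a matter of preference. Only the absence of any rule is the defect.

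**Conclusion.** The concern holds, as something that should be fixed. Neither document says how two between-laser tests of one primary outcome combine into a conclusion. If either visit counts, the primary type I error is about 6.7% to 8.3% with the exact Mann-Whitney test and 7.3% to 9.2% with the normal approximation. If both are required, or one visit is named first, it is at most 4.5% exact or 5.0% approximate.

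These sizes rest on the assumed equal split, two-sided testing and correlation of 0.5 to 0.9. The direction does not: two tests at a nominal 5% with an either-visit rule exceed 5% unless they always agree or each has a true size well below its nominal level. The plan's silence on the rule is read directly from the text.

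**What to change.** Before any comparison by arm, amend SAP sections 3 and 4 to state:

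1. The primary test is the between-arm difference in VAS change from baseline to one visit, identified in the protocol's terms. The end-of-treatment assessment is one example; the 1-month assessment would serve equally if the sponsor prefers it.
2. The VAS change at the other visit is tested at 0.05 only if the first test is significant.
3. The test used for this comparison, since section 4 names none for the case where normality is not rejected. The Mann-Whitney test already in section 4 could be kept whatever the Shapiro-Wilk result.
4. Which protocol assessment the SAP means by post-treatment.

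A both-visits rule or an alpha split would also control the error. A fixed sequence is suggested because it keeps the full 0.05 for one named visit. Its cost is that a difference present only at the second visit could not be claimed.

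The amendment is a few sentences and needs no extra patients or data, provided the arms have not been compared. The documents do not settle that. SAP section 9 says only "This SAP was finalized and approved prior to database lock and commencement of statistical analyses". If the comparison has already been made, the report should say so, give both visits, and label any ranking of them as post hoc.

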### Aim of the study

To assess the effect of low level laser therapy (LLLT) to relieve pain in myofacial pain syndrome (MPS), caused by fatigue of temporalis and masseter muscles, by using 980nm diode laser, and compare between diode laser 980nm and diode laser 635nm

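### The aim asks whether laser relieves pain, but the design can only compare 980 nm with 635 nm, and no time point or rule decides that comparison

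*SAP*

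**What the plan says.** **Aim and objective.** The protocol's Aim of the study has two parts. The first reads "To assess the effect of low level laser therapy (LLLT) to relieve pain in myofacial pain syndrome (MPS"); the second is to compare the 980 nm and 635 nm diode lasers. SAP section 2 has "Primary Objective: To evaluate the effectiveness of photobiomodulation therapy using diode lasers (980nm vs 635nm) in reducing myofascial pain". The SAP title and the protocol's PICO are comparative.

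**Arms.** Under The clinical procedure, group 1 receives 635 nm and group 2 receives 980 nm, both active. No sham or untreated group is described. There are 30 patients in two groups; the split is not given.

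**Primary outcome.** SAP section 3: "Primary Outcome: Change in pain intensity measured by the Visual Analog Scale (VAS) from baseline to post-treatment and follow-up".

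**Tests.** SAP section 4 opens with a normality check and then "If data are not normally distributed, non-parametric tests will be applied"; no test is named for normal data. Next comes "Within-group comparisons across time points (baseline, post-treatment, follow-up) will be analyzed using the Friedman test", with Bonferroni-corrected post-hoc pairs, and then "Between-group comparisons will be conducted using the Mann-Whitney U test on change scores". The threshold throughout is 0.05. Section 5 adds an effect size for each, including "Kendall's W for Friedman test results (within-group changes").

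**Visits.** The protocol's Patient assessment lists four occasions: before treatment, after laser applications, at the end of treatment, and one month later. It describes the VAS only as taken just before therapy.

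**The concern.** There are two linked gaps.

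First, part of the aim is an absolute question (does laser relieve this pain?), and no arm goes without laser. The only planned analysis that bears on that question is the within-group Friedman test, which is run at 0.05, carries its own effect size and has no label limiting its use. A reader who finds significant falls in both arms could report that laser works. A reader who finds one arm significant and the other not could report that one wavelength works. Neither conclusion would follow.

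Second, the question that the design can address is not tied down. The primary outcome yields two between-group VAS tests, one at post-treatment and one at follow-up. Nothing says which decides, whether one suffices or whether both are needed. The stated Bonferroni correction belongs to the within-group pairs and does not reach these two tests. The SAP's post-treatment time point is also not tied to one visit, because the protocol lists the assessment after laser applications separately from the one at the end of treatment. The more favourable result could be presented as primary after the fact.

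**Working it through.** The documents give no power, SD or error-rate figure to reproduce. The attribution problem is settled by the text; the time-point problem can be sized under stated assumptions.

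**1. What the design identifies.** Change in the 635 nm arm = laser effect (635) + non-specific change. Change in the 980 nm arm = laser effect (980) + non-specific change. If non-specific change is the same in both arms, subtraction leaves effect (980) minus effect (635). Neither effect can be recovered alone. A Friedman test in one arm tests the whole sum.

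**2. Illustration of the within-group risk (not an error rate of the plan).** Assumptions: 15 per arm, three visits, SD 2 VAS points, identical arms, pain falling in both for any reason.
- With between-visit correlation 0.3-0.7, Friedman is significant in about 26-57% of arms for a 1-point fall and about 78-99% for a 2-point fall.
- A 1-point fall is 0.5 SD. At correlations 0.5 and 0.7, simulation gave 0.361 and 0.536 significant per arm, and exactly one arm significant in 47% and 51% of trials. Check with independent arms, 2p(1 - p): 2 × 0.361 × 0.639 = 0.46; 2 × 0.536 × 0.464 = 0.50.

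So with no wavelength difference at all, a split result is about as likely as not in this setting.

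**3. Two between-group time points.** Inputs: alpha 0.05 (SAP section 4; two-sided assumed), two time points (SAP section 3), 15 per arm (assumed equal split of 30), arms truly equal.
- One Mann-Whitney test: about 4-5% false positives in simulation.
- Upper reference if the two tests were independent: 1 - (1 - 0.05)² = 0.0975.
- If all three visits are equally correlated at rho, the two change scores share the baseline and correlate at (1 - rho) / (2(1 - rho)) = 0.5, whatever rho is. Varying that correlation directly on normal change scores:

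| Correlation of the two change scores | Either significant, with / without continuity correction |
|---|---|
| 0.5 | 0.083 / 0.092 |
| 0.7 | 0.077 / 0.084 |
| 0.9 | 0.067 / 0.074 |

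Clipping or rounding the VAS and changing the size of the common fall moved the 0.5 row within 0.080-0.095.
- Both significant: P(both) = 2 × P(one) - P(either). With P(one) = 0.05 and no continuity correction, this is 0.100 - 0.092 = 0.008 at correlation 0.5 and 0.100 - 0.074 = 0.026 at 0.9. Direct simulation gave about 0.6-2.7%.

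**4. After the fix.** One test at one named time point returns the rate to about 4-5%.

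**The case against.** The strongest reply is that the plan is already comparative. The SAP title, the bracket in its primary objective and the PICO all set 980 nm against 635 nm, and only the protocol aim clearly states an absolute effect. Sections 3 and 4 read together identify Mann-Whitney on VAS change as the between-group test. The SAP never ties the Friedman test to an objective, and within-group tests are common secondary output. All of this stands. A reader might infer that no between-group test is planned, or that the Friedman test has been made the efficacy test; the documents support neither. What remains is that the comparison is not designated as deciding, and nothing stops the within-group results from being used for the first half of the aim.

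A second reply is that the primary outcome joins its two time points with the word and, which can be read as requiring both. On that reading the false-positive rate is below 5%. This also stands, and it rules out a claim of certain inflation. It does not remove the need to state the rule, since the SAP supports either reading.

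Third, the SD, correlations and equal split are not in the documents. That is correct. The percentages size the ambiguity; the point itself rests on the text.

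Finally, the missing test for normal data and the lack of a confidence interval in VAS points are lesser matters and do not carry the point.

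**Conclusion.** The point holds and should be fixed. With two active arms, the trial can address only the difference between wavelengths; the effect of laser itself is not identifiable, and unlabelled within-group tests leave room for claiming it. The between-group VAS test exists but lacks primary status and a deciding time point or rule.

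If either time point may count, the false-positive rate is about 8-9.5% at a change-score correlation of 0.5 and about 6.6-7.4% at 0.9, against a nominal 5%. If both are required, it is about 0.6-2.7%. A reader might conclude that the plan's type I error is inflated; the text does not establish that, only that the rate depends on an unstated choice.

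These figures assume 15 per arm, two-sided tests and arms that are exchangeable apart from wavelength. The available text says only that patients were divided into two groups. Front pages were removed, so nothing is concluded here about how patients were allocated. The attribution argument needs none of these numbers.

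**What to change.** 1. **Objective.** Reword the protocol aim and SAP section 2 as the comparison of VAS change between 980 nm and 635 nm.
2. **Deciding test.** State in SAP section 4 that the between-group Mann-Whitney test of VAS change decides the primary objective, which also closes the open normality branch for this outcome. Name one time point, tie it to one visit in the protocol's Patient assessment, and confirm that the VAS is recorded at that visit. Alternatively, at the sponsor's choice, require both time points or adjust for two tests.
3. **Timing of the change.** Set and date this before outcome data by group are seen. The protocol describes its procedures in the past tense, and SAP section 9 says "This SAP was finalized and approved prior to database lock and commencement of statistical analyses", so this may no longer be possible. In that case report both time points and describe the choice as post hoc.
4. **Within-group results.** Label the Friedman tests, their post-hoc pairs and Kendall's W as descriptive of change over time and not as evidence of laser efficacy.

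Optional: report the between-group difference in VAS points with a 95% confidence interval beside the rank-biserial correlation.

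**Cost.** A wording amendment to the aim and to an approved SAP, with no added arm, visit or patient. The sponsor gives up a claim that laser itself works, and either one time point becomes secondary or the success rule becomes stricter.

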### Materials and methods

#### Patient assignment and blinding:

30 PATIENTS. Divided in to 2groups.

Comparison between two groups , First one, By using diode laser 635nm (flat top handpiece)

And other group by using diode laser 980nm (flat top handpiece).

The hand-pieces fixed at distances of 3 mm and 15 mm from the power meter, only the FT profile hand-piece had a constant power output, which was comparable to the contact mode.

Introsion criteria:-patients with Tmds due to stress,medically free, not to resort to self-medication during the study period.

Extrusion criteria:-patients with bruxisms, erosions,medically free,diabetics

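### The within-arm analysis stacks Bonferroni on a Friedman gate: valid, but needlessly conservative if exactly three visits are analysed

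*SAP*

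**What the plan says.** SAP section 4 names the overall test: "Within-group comparisons across time points (baseline, post-treatment, follow-up) will be analyzed using the Friedman test". The second half of that sentence sets the step that depends on its result: "followed by post-hoc pairwise comparisons with Bonferroni correction if significant differences are detected". The significance level is 0.05. Sidedness, the pairwise test and the Bonferroni divisor are not given. With three time points there are three pairs, so the divisor is presumably 3. No reason is offered for using both a gate and a correction.

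The two lasers are compared separately: "Between-group comparisons will be conducted using the Mann-Whitney U test on change scores".

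The protocol gives the sample size as "30 PATIENTS. Divided in to 2groups", without stating an equal split. Its Patient assessment section lists four assessment times, "before treatment ,after laser applications ,at the end of treatment , and 1 month after the laser applications", where the SAP analyses three.

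**The concern.** A significant Friedman test and a Bonferroni correction each protect against false positives among the visit pairs. With three visits either one is enough, so using both pays twice. In an arm of about 15 patients, a real change from baseline, or a real difference between the end of treatment and the 1-month visit, could be reported as not significant for that reason alone. The primary outcome is VAS change from baseline to post-treatment and follow-up, so readers are likely to use these pairwise results to judge whether relief lasts.

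**Working it through.** **Inputs.** Level 0.05 (SAP section 4; two-sided assumed). Three visits, hence three pairs (SAP section 4). Thirty patients in two groups (protocol, Patient assignment and blinding), so 30/2 = 15 per arm if split equally. The documents contain no power figure, SD or expected effect, so there is nothing to reproduce, and effects are shown over a range in SD units.

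**Logic.** Let A be baseline = post-treatment, B baseline = follow-up, and C post-treatment = follow-up, each meaning equal distributions. If any two hold, so does the third. Only three cases can therefore produce a false positive or rule one out:

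- None true: no false positive is possible.
- Exactly one true: a false positive needs that one pair test to reject, which has probability at most 0.05.
- All true: a false positive needs the Friedman gate to reject, which has probability at most 0.05.

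So gate at 0.05, then pairs at 0.05, controls family-wise error at 0.05. The SAP rule tests each pair at 0.05/3 = 0.0167 after the same gate. It can never reject a pair that the closed procedure does not.

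**Family-wise error by simulation** (100,000 arms of 15, normal data, within-patient correlation 0.5, exact Wilcoxon signed-rank pairs):

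| Truth | SAP rule | Gate, then 0.05 |
|---|---|---|
| All visits equal | 2.4% | 4.0% |
| Only baseline differs, 0.5 SD | 1.3% | 3.5% |
| Only baseline differs, 1.0 SD | 1.5% | 4.7% |
| Only baseline differs, 3 SD | 1.6% | 4.8% |

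With all visits equal, Bonferroni without the gate gives 4.2%, and neither device gives 12.3%. Some control is needed; two layers are not.

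**Power per pair** (Wilcoxon; the 1.0/0.6 SD row is from a separate run of 60,000 arms):

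| True pattern | Pair | SAP rule | Gate, then 0.05 | Loss, points |
|---|---|---|---|---|
| Sustained fall 0.5 SD | baseline vs either later visit | 18.9% | 26.7% | 7.8 |
| Sustained fall 0.8 SD | same | 56.2% | 66.9% | 10.7 |
| Sustained fall 1.0 SD | same | 80.2% | 87.6% | 7.4 |
| Sustained fall 1.5 SD | same | 99.4% | 99.8% | 0.4 |
| Falls of 1.0 SD, then 0.6 SD | baseline vs follow-up | 34% | 51% | 17 |
| Falls of 0.5 SD, then 1.0 SD | baseline vs post-treatment | 22.8% | 38.7% | 15.9 |
| Same | baseline vs follow-up | 74.7% | 78.6% | 3.9 |
| Falls of 1.4 SD, then 2.0 SD | post-treatment vs follow-up | 35.4% | 55.9% | 20.5 |

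The loss is largest for the smaller contrast in an arm where another contrast already opens the gate, because Bonferroni is then the binding constraint.

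**If the pairs are compared by a Dunn-type test on the Friedman ranks**, which the SAP does not exclude, the sustained-fall losses are 27.1 − 17.3 = 9.8 points at 0.5 SD, 64.4 − 47.2 = 17.2 at 0.8 SD and 84.5 − 68.7 = 15.8 at 1.0 SD.

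**Four visits.** The logic above fails: if only baseline differs, three pair nulls remain true after the gate opens. With a 3 SD baseline difference, gate plus unadjusted Wilcoxon pairs gives a family-wise error of 12.2%, against 1.9% with Bonferroni across the six pairs.

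**The case against.** *It is a valid, prespecified rule.* This stands. A reader might infer that the SAP's procedure is wrong or inflates error; it does neither. The case for change is only that an equally protected rule rejects everything the SAP rule does and more.

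*It does not touch the main question.* This also stands. The comparison of the two lasers is a Mann-Whitney test on change scores. There is no sham or untreated arm, so a within-arm p-value cannot separate laser effect from natural course or regression to the mean. Gaining within-arm power does not strengthen the evidence for either wavelength.

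*Three visits is not settled.* This stands and limits the remedy. A reader might infer that Bonferroni can simply be deleted. The protocol already lists four assessments, and with four the unadjusted step would not hold the error rate.

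*The gain can be overstated.* In the pattern with falls of 1.0 and 0.6 SD, a rank-sum post-hoc with Bonferroni detects baseline versus follow-up about 21% of the time, and one might set that against the 51%. That comparison mixes two changes and assumes a pairwise test that the SAP never names. The part due to Bonferroni is 34% versus 51%.

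*The error guarantee was checked on normal data.* This is fair: the simulations had no ties, floor effects or dropout. With equal medians and one skewed visit, the closed procedure rejected in 15% of arms and the Bonferroni version in 12%. The limitation is shared, so it does not favour the SAP rule.

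*There are many outcomes and two arms.* True, but Bonferroni across visit pairs does not address that multiplicity either.

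**Conclusion.** The point holds as a minor efficiency note. If the three visits named in the SAP are the ones analysed, the Bonferroni step adds no needed protection. It takes family-wise error down to 2.4% or less with Wilcoxon pairs. The power lost is about 7 to 11 points for a sustained fall of 0.5 to 1.0 SD, about 16 to 20 points for the smaller contrasts when the post-baseline visits differ, and negligible for a sustained fall of 1.5 SD.

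These sizes rest on 15 patients per arm, two-sided tests, normal data, correlation 0.5, complete follow-up and effects chosen for illustration. The closed-testing argument itself does not depend on the effect sizes, but it does depend on there being three visits. The documents do not support reading this as a flaw in the comparison of the two lasers, or as an invalid analysis.

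**What to change.** Before outcome data are analysed by arm, confirm which assessments enter the Friedman test and reconcile the SAP's three with the protocol's four. Then replace the post-hoc clause in SAP section 4, as a dated amendment, with:

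> If the Friedman test is significant at 0.05, visit pairs are compared by Wilcoxon signed-rank tests. With three analysed visits, each pair is tested at 0.05 (closed testing). If four visits are analysed, a Holm or Shaffer step-down adjustment replaces Bonferroni.

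The cost is a short wording change plus the decision on visits; no extra patients or measurements are needed. The error guarantee remains per arm and per outcome, with no cover across the two arms or the several outcomes. The within-arm results should still be reported as uncontrolled before-after comparisons.

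### The 980 nm versus 635 nm comparison rests on a Mann-Whitney test of change scores; no baseline-adjusted VAS difference with a 95% CI at a named visit is planned

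*SAP*

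**What the plan says.** SAP section 3 defines the primary outcome as "Change in pain intensity measured by the Visual Analog Scale (VAS) from baseline to post-treatment and follow-up". That is two time points, and neither is designated primary.

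SAP section 4 then states: "Between-group comparisons will be conducted using the Mann-Whitney U test on change scores". The sentence covers every outcome, VAS included. The only between-group effect measure, in section 5, is "Rank biserial correlation (r) for Mann-Whitney U test results (between-group comparisons". Section 4 also says "If data are not normally distributed, non-parametric tests will be applied", which implies a parametric route for normal data. None is named, and the Mann-Whitney sentence carries no condition.

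The protocol has no analysis methods. Under Patient assessment it gives the schedule as "The patients were evaluated before treatment ,after laser applications ,at the end of treatment , and 1 month after the laser applications.(18", and on the baseline measurement it says "A visual analog scale (VAS) was used for calculating pain grade right before our therapy". Pain is scored from 0 to 10. On numbers and allocation, the supplied text under Patient assignment and blinding says only "30 PATIENTS. Divided in to 2groups". Neither document mentions a VAS difference in points, a confidence interval, a baseline covariate or a model.

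**The concern.** The comparison of the two lasers is the trial's question, and it rests on 30 patients. As planned, it yields a p-value and a rank-biserial r. Neither tells a clinician how many VAS points separate the lasers or how uncertain that figure is. In a trial this small, a non-significant p could easily be misread as equivalence.

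Baseline VAS enters only by subtraction, which fixes its slope at 1. ANCOVA estimates the slope. Under random allocation this usually narrows the interval and removes the effect of a chance baseline gap.

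The visit is also open. The protocol lists three post-baseline assessments, so the SAP's post-treatment point could be the one following laser application or the one when treatment ends. Testing both SAP time points at 0.05 without correction would give a familywise error of 1 − 0.95² = 9.75% if the tests were independent. Visits in the same patient are correlated, so this is an upper illustration.

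**Working it through.** **Plan's own figure.** There is none to reproduce: the documents give no power, SD, correlation or target difference.

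**Inputs.** From the documents: N = 30, two groups, alpha 0.05, VAS 0–10. Assumed: 15 per arm, random allocation, two-sided test, no dropout, baseline SD s0 = 2, true difference 2 points, baseline-to-visit correlation rho = 0.3/0.5/0.7, and k = post-treatment SD / baseline SD from 0.75 to 1.5 (s1 = k × s0).

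**Formulas.**
- Var(change) = (s0² + s1² − 2·rho·s0·s1) × 2/15
- Var(ANCOVA) = s1²(1 − rho²) × 2/15 × (1 + 1/(N − 4)). The last factor, 1 + 1/26 = 1.038, is the cost of estimating the slope.
- Information lost by the change score = 1 − Var(ANCOVA)/Var(change)

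**Example, k = 1, rho = 0.5.** Var(change) = (4 + 4 − 4) × 2/15 = 0.533. Var(ANCOVA) = 4 × 0.75 × 2/15 × 1.038 = 0.415. Loss = 1 − 0.415/0.533 = 22%.

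**Loss and simulated power** (20,000 trials per setting, Monte Carlo SE at most 0.35 points; each cell is rho 0.3 / 0.5 / 0.7):

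| k | Information lost, % | Mann-Whitney on change, % | t-test on change, % | ANCOVA, % |
|---|---|---|---|---|
| 0.75 | 52 / 46 / 42 | 66.9 / 80.0 / 94.5 | 70.7 / 83.4 / 96.0 | 95.2 / 97.9 / 99.8 |
| 1 | 32 / 22 / 12 | 57.2 / 71.3 / 90.7 | 60.9 / 75.3 / 92.6 | 77.2 / 84.6 / 95.2 |
| 1.25 | 18 / 7 / −2 | 46.2 / 59.8 / 79.9 | 50.1 / 63.8 / 83.2 | 58.3 / 67.1 / 82.5 |
| 1.5 | 10 / 0 / −4 | 37.7 / 47.7 / 65.6 | 40.7 / 51.6 / 69.3 | 44.2 / 51.9 / 67.9 |

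A negative loss means ANCOVA is slightly less precise. At k = 1, 30 adjusted patients are worth 30/(1 − loss), about 44/39/34 unadjusted ones. The t-test column separates two sources of gain. At k = 1, baseline adjustment adds 16/9/3 points (ANCOVA minus t-test) and leaving ranks on normal data adds 4/4/2 (t-test minus Mann-Whitney).

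**Interval width.** At k = 1 the expected 95% CI half-width is 1.75/1.48/1.15 VAS points for the difference in mean change and 1.44/1.31/1.08 for ANCOVA.

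**Chance imbalance.** SE of the baseline gap = 2 × √(2/15) = 0.73, so P(gap above 1 point in either direction) = 17%. Each point of gap shifts the change-score difference by rho·k − 1: 0.7/0.5/0.3 points in size at k = 1, and about 0 at k = 1.5 with rho 0.7.

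**Robustness.**
- Whole-number VAS clipped to 0–10 (baseline mean 6.5, SD 1.5; post-treatment means 4 and 2, SD 2): Mann-Whitney 64/77/92%, ANCOVA 76/82/93%.
- Type I error was 4.3–5.5% for every method.
- Floor, equal arms (post-treatment mean 1.5, 31% zeros): ANCOVA type I error 4.8–5.2%.
- Floor, unequal arms (means 2.5 and 0.5; 16% and 50% zeros): ANCOVA CI coverage 94.8–95.2%; power 72/79/89% against 54/66/83% for Mann-Whitney.

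**The case against.** The planned test is valid under random allocation, and a change score does use the baseline. A Hodges-Lehmann shift with a 95% CI would supply VAS points and an interval without replacing the test. That is true, but it would not adjust for baseline, so it meets half of the concern.

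The efficiency gain rests on assumed values. This stands. In the whole-number run, where k is about 1.2 to 1.3, adjustment itself adds only 9/3/0 power points, and at k = 1.5 with rho 0.5 its information gain is nil. A 2-point difference between two active lasers is generous: at 1 point and k = 1, power is 19/23/38% for Mann-Whitney and 27/33/45% for ANCOVA, low either way. The 17% imbalance figure falls to 6.8% if baseline SD is 1.5.

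The sharpest point is that ranks can win on heavy tails. With t-distributed errors on 3 df, Mann-Whitney on change against ANCOVA gives 68/85/97% against 83/87/94% at k = 1, and 56/72/88% against 56/62/77% at k = 1.5, a reversal of up to about 11 points. Those errors are unbounded, and a 0–10 scale cannot produce them. The result is a reason to keep Mann-Whitney as a sensitivity analysis rather than as the primary one.

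The undesignated visit and the allocation method are separate specification gaps that ANCOVA alone would not close. The fix therefore lists them separately.

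**Conclusion.** The concern holds. The plan provides no VAS-point difference, confidence interval, baseline covariate or single primary visit for its main comparison. That absence depends on no assumption.

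The size of the precision loss does. For normal data with equal SDs at the two visits and a 2-point difference, the planned test gives up 20/13/5 power points to ANCOVA at rho 0.3/0.5/0.7, most of it from the unused baseline at the two lower correlations. The gain is larger if VAS becomes less variable after treatment. It is nil or slightly negative at k = 1.25 with rho 0.7, and at k = 1.5 with rho 0.5 or above.

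The precision argument requires random allocation, which the supplied methods text does not state, though removed pages may. Without it, the change-score and adjusted contrasts estimate different quantities; the need for a difference in points with an interval remains. This is a change the plan should make, not an error that invalidates the planned test.

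**What to change.** Amend SAP section 4 as follows.

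1. Name one primary VAS visit and say which assessment in the protocol's Patient assessment section it is.
2. Replace the between-group sentence for VAS with: *The primary between-group analysis is an analysis of covariance of VAS at the primary visit on group and baseline VAS. The 980 nm minus 635 nm adjusted difference is reported in VAS points with its 95% CI, whatever the Shapiro-Wilk result.*
3. Keep Mann-Whitney on change as a sensitivity analysis, ideally with a Hodges-Lehmann interval; Quade rank ANCOVA is optional. A mixed model over visits is optional, as a missing-data sensitivity analysis only, and should state which assessments it includes.
4. State how patients were allocated. If not at random, do not present the adjustment as a gain in precision.

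The cost is a dated amendment and one SPSS UNIANOVA command. It needs no new data and the same patients as the planned test (baseline plus that visit). The statistical price is about 4% of variance for the estimated slope and a reliance on roughly normal residuals. SAP section 9 describes the plan as final, so the amendment must predate any sight of between-group data. If those data have been seen, label the ANCOVA post hoc and still report the difference with its interval.
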